Our study plans to randomize treatment naive patients with vestibular migraine to an 8 week trial of an escalating dose of either nortriptyline or topiramate followed by an 8 week crossover to the other drug if patient is willing, if patient wants to stay on first medication we will just continue to follow. During the first 8 weeks if there is an intolerance to the first drug they can be switched to the other drug at any point and then followed on that medication for the remainder of the study. Response to therapy will be quantified by the Migraine Specific Quality of Life (MSQ) and Dizziness Handicap Inventory (DHI) administered at multiple time points during the study. Three groups of patients that will be eligible for the study will include 1)Patients with Neuhauser dVM; 2)Patients with pVM; and 3) Patients with dizziness that falls outside the Neuhauser criteria (non-Neuhauser vestibular migraine or nNVM).

Our hypothesis is that even patients with dizziness outside of the Neuhauser dVM and pVM spectrum will respond to treatment for vestibular migraine, and thus likely have migraine as a cause of their dizziness. Previous research by our group has suggested that such patients do in fact respond to migraine therapy1. A second goal of the study is to evaluate the comparative efficacy of nortriptyline and topiramate in the treatment of these three subgroups of patients with vestibular migraine.

Page numbers from a sponsor's protocol/grant may be referenced in 2b and 2c.

b) **List your research objectives (specific aims & hypotheses of the study).**

The primary goal of the study is to evaluate the comparative effectiveness of migraine diet, nortriptyline and topiramate in the treatment of these three subgroups of patients with vestibular migraine. A secondary hypothesis is that even patients with dizziness outside of the Neuhauser dVM and pVM spectrum will respond to treatment for vestibular migraine, and thus likely have migraine as a cause of their dizziness. Previous research by our group has suggested that such patients do in fact respond to migraine therapy ([name], 2012).

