The attached flow chart illustrates the study design (Figure 1). After identification and trial entry, we will complete intake questionnaire to determine what type of vestibular migraine category the patients qualify for, a standard of care office visit with history and physical (Standard of Care) to review symptoms and previous treatment, patients height and weight (standard of care) will be obtained. Patients will complete a standard of care audiology assessment, and the following questionnaires: MSQ (Migraine Symptom Questionnaire) Version 2.1, DHI (Dizziness Questionnaire) , C-SSRS (Columbia Suicide Severity Rating Scale) and the MoSQ (Motion Sensitivity Questionnaire). All drug naive patients will undergo a one month lead in of treatment involving dietary and behavioral control of migraine. Emphasis will be given to cessation of known migraine triggers such as caffeine, sodas, chocolates, alcohol (especially red wine) and aged cheeses. Patients who have complete control of their symptoms with diet and behavior modification alone will be followed for a total of 4 months to determine the durability of symptom relief. Patients who fail behavior modification during the 2 to 4 month time point can chose to enter the drug treatment portion of the study, as defined below.

At the one month point, patients will be brought into the clinic for a office visit or contacted by phone and will complete medical history, MSQ V2.1, DHI, C-SSRS and the MoSQ, then will be randomization to either nortriptyline or topiramate will occur. Randomization will occur by opening the lowest numbered of a stack of envelopes which will contain a randomly preselected

Protocol Title:

A Prospective randomized cross-over trial of nortriptyline and topiramate in the initial treatment of vestibular migraine

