The response to therapy will be assessed during monthly visits with the use of the MSQ, DHI and MoSQ questionnaires. Patients will be provided compensation for participating in the study. \$60 dollars will be paid to each patient for each month that they participate in the study. Our goal is to recruit 100 patients over the span of one year.

Data which will be collected include age, sex, height, weight, body mass index (BMI), prior head MRI or CT, results of vestibular testing, family history of migraine. A careful history will focus on vestibular migraine comorbidities such as visual scotoma, ability to ride in the back seat of a car, and history of "sinus pain".

Patients will be identified as having one of three subtypes of vestibular migraine, based on their symptoms and history as obtained during their initial visit.

Criteria for Neuhauser definite vestibular migraine (dVM): (Neuhauser, 2009):

1. Episodic vestibular symptoms of at least moderate severity.
2. Current or previous history of migraine according to the 2004 criteria of the International Headache Society (IHS)
3. One of the following migrainous symptoms during 2 or more attacks of vertigo: migrainous headache, photophobia, phonophobia, visual aura, or other aura
4. Other causes ruled out by appropriate investigations

Criteria for probable vestibular migraine (pVM):

1. Episodic vestibular symptoms of at least moderate severity
2. One of the following
 - A. current or previous history of migraine according to the 2004 criteria of the IHS
 - B. migrainous symptoms during vestibular symptoms
 - C. migraine precipitants of vertigo in > 50% of attacks: food triggers, sleep irregularities, or hormonal change
 - D. Response to migraine medications in more than 50% of attacks
3. Other causes ruled out by appropriate investigations

Protocol Title:

A Prospective randomized cross-over trial of nortriptyline and topiramate in the initial treatment of vestibular migraine

Criteria for (non-Neuhauser vestibular migraine or nNVM) will include those patients who do not fit the criteria for dVM and pVM but are felt by the investigator to have underlying migraine as a possible cause of their dizziness. This includes patients with a remote history of migraines, those with visual auras without headache, those with recurring self-described "sinus pain" and those with significant motion intolerance, either to their own head motion or motion in their surroundings.

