Due to known drug interactions, patients taking the following medications will be excluded. Nortriptyline: monoamine oxidase inhibitors (MAO) such as phenelzine. Patients on oral contraceptives will be asked to use a secondary method as nortriptyline can reduce the effectiveness of oral contraceptives.

Topiramate: acetazolamide (kidney stones), digoxin

An electronic health record (EPIC) will be used for secure collection of all patient data. Questionnaires filled out by patients will be scanned into EPIC.

A sample size of 100, which nets 90 subjects into the randomized medication trial (two equal groups of 45 subjects each), yields a power of 82% to detect a difference in patient-reported effectiveness/acceptability between the nortriptyline and topiramate groups after two months of medication use. This sample size estimate assumes 60% of subjects using nortriptyline report it as effective/acceptable, in contrast to half as many subjects (or 30%) using topiramate. The power calculation is based on a two-sized Z-test with pooled variance and targeted significance level (alpha) of 0.05. The expected difference in outcome between the two groups is based on our prior research ([name], 2012).

Adverse effects of the two drugs will be assessed. Specifically, the following known side effects will be asked about and recorded.

Nortriptyline: somnolence, weight gain, dry mouth, blurred vision

Topiramate: Weight loss, parasthesias, forgetfulness, nausea, diarrhea, fatigue

The subjects will be allowed to maintain therapy or taper off the drugs. It is anticipated that those that derive benefit from the drugs will choose to stay on them. All patients will have the option of remaining under our care outside of the study.

c) If the proposed study is a clinical trial where a drug, vaccine, device or other treatment is compared to a placebo group or comparison treatment group, what are the guidelines or endpoints by which early decisions regarding efficacy or lack of efficacy can be made? For example, it may be reasonable to stop enrollment on a study when efficacy has already been clearly demonstrated, to avoid unnecessary enrollments of additional subjects. Alternatively, it may be reasonable to stop enrollment when it is clear that efficacy will never be demonstrated, given the statistical power of the study as designed. Describe the guidelines that are in place to assist in making these determinations, if relevant to the proposed study.

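### Randomisation runs from one envelope stack with no stated stratification by migraine subtype, so balance within subtypes is left to chance; the likely loss is modest and the remedy is cheap.

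*Combined protocol and SAP*

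**What the plan says.** Section 3b describes the allocation in one place: "Randomization will occur by opening the lowest numbered of a stack of envelopes". Each envelope holds a card, chosen at random in advance, that names the drug. The section does not say how the card sequence was generated. It mentions no blocks, no strata and no separate stacks.

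Subtype is known in time to be used. Section 3b has an intake questionnaire settle the category at trial entry, and later says patients are classified "based on their symptoms and history as obtained during their initial visit". Most patients then spend a month on diet and behavioural measures before randomisation. The exception is the small group already on a strict migraine diet, who go straight to the drug phase.

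Subtype also matters to the aims. Section 2b opens by making the primary goal a comparison of diet, nortriptyline and topiramate "in the treatment of these three subgroups of patients with vestibular migraine". The lay summary in 2a and the second paragraph of 2b instead rank the drug comparison in these subgroups as a second goal. Section 3d plans a subgroup analysis by subtype, and a check of baseline attributes for confounding. The sample size paragraph in 3b covers only the overall comparison, in "two equal groups of 45 subjects each".

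**The concern.** A single stack can at best balance the two drugs overall. It does nothing to balance them within dVM, pVM or nNVM, although that is where the protocol says it wants to compare them.

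Two consequences need separating. If the arms differ in subtype mix, the pooled comparison can be adjusted for subtype and little is lost. A comparison inside one subtype is different: its variance is proportional to 1/n1 + 1/n2 for the numbers actually allocated there, and no later model changes those numbers. A lopsided subtype gives a less precise answer to a stated question.

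There is also some cost to credibility. Treatment is open label, the powered outcome is patient-reported, and nNVM membership depends partly on investigator judgement. Arms that visibly differ in diagnostic mix would invite questions that stratification avoids.

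**Working it through.** **Inputs from section 3b.** 90 randomised, 45 per arm. The calculation "assumes 60% of subjects using nortriptyline report it as effective/acceptable", against 30% for topiramate. Test: "two-sized Z-test with pooled variance" (read as two-sided). Level: "targeted significance level (alpha) of 0.05". One envelope stack, sequence method not given.

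**Assumed, because the documents do not give them.** Subtype sizes among the 90. Sequence type: either simple randomisation, or a stack fixed at 45 cards per drug, which the wording about equal groups allows.

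**1. The plan's own figure.** The protocol says the sample "yields a power of 82% to detect a difference in patient-reported effectiveness/acceptability".

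Power = Φ[(|p1 − p2| − 1.96·s0)/s1], with s0 = √[p̄(1−p̄)(1/n1 + 1/n2)] and s1 = √[p1(1−p1)/n1 + p2(1−p2)/n2].

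With 45 per arm, p̄ = 0.45, s0 = 0.1049 and s1 = 0.1000. Then (0.300 − 0.2056)/0.1000 = 0.944 and Φ = 82.8%. Exact enumeration of the same test gives 81.8%. The stated 82% reproduces.

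**2. Chance that one subtype splits 2:1 or worse.** For a subtype of size n, the number on nortriptyline is Binomial(n, ½) under simple randomisation. With a fixed stack it is hypergeometric (n drawn from 90, 45 of each drug).

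| n | Simple | Fixed 45/45 |
|---|---|---|
| 30 | 9.9% | 4.3% |
| 24 | 15.2% | 9.4% |
| 15 | 30.2% | 25.8% |

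**3. Chance that at least one of the three subtypes does so.**

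| Sizes | Simple | Fixed 45/45 |
|---|---|---|
| 30/30/30 | 27% | 11% |
| 45/30/15 | 39% | 28% |
| 60/20/10 | 43% | 36% |

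Where n is not divisible by 3, the event is the nearest split at least as uneven as 2:1 (6/14 for n=20, 3/7 for n=10).

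**4. Cost of a 2:1 split when it happens.** For n=30, (1/20 + 1/10)/(1/15 + 1/15) = 0.1500/0.1333 = 1.125. Variance rises by 12.5%, and the standard error by √1.125 − 1 = 6%.

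**5. Expected cost.** Precision relative to an even split is 4f(1−f), where f is the share on one drug. Its mean under simple randomisation is 1 − 1/n, a loss of 3.3% at n=30 and 6.7% at n=15, which is one patient's worth at any n. With a fixed stack the loss is (1/n)(90−n)/89: 2.2% at n=30 (about 0.7 patient) and 5.6% at n=15 (about 0.8 patient).

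**6. Power inside a subtype, 60% vs 30%.** For n=30 split 15/15, s0 = 0.1817 and s1 = 0.1732. Then (0.300 − 0.3560)/0.1732 = −0.324, giving 37.3%. Split 10/20 it is 35.0% or 33.1%, depending on which drug has the 10. Averaged over possible splits it is 36.3% (simple) or 36.6% (fixed). Reaching 80% would take 42 per arm, or 84 patients in that one subtype.

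**7. What stratified blocks would do.** Blocks of four (size assumed) limit the within-subtype difference to two patients. The worst case at n=30 is 14/16, which keeps 4·14·16/900 = 99.6% of even-split precision.

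**The case against.** The strongest reply is that this matters little. Averaged over possible allocations, one stack costs at most about one patient per subtype and roughly one point of power at n=30. The 2:1 split is a tail event, and even then it costs about 1 to 4 points. The real weakness of the subtype comparisons is their size, which three stacks leave untouched. All of this stands, and it sets the size of the point.

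Other parts also stand:

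- The wording about equal groups is compatible with a fixed 45/45 stack, which at n=30 less than halves the chance of a bad split. Both scenarios must be shown.
- The goal ranking is inconsistent, and the power calculation concerns only the pooled comparison.
- The crossover component compares each patient with themselves and depends little on the initial split.
- Adjusting for subtype deals with chance imbalance in the pooled result. Section 3d goes part of the way with its confounding check, but does not commit to a subtype term.
- The flow chart and grant application are attachments not available here, so stratification described only there cannot be excluded.
- Separate stacks let a partly discretionary label decide which envelope is opened.

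What the reply does not remove is that within-subtype precision is set at allocation and cannot be repaired afterwards. Under either ranking, the subtype comparison remains a stated goal with a planned analysis.

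A reader might infer that the single stack biases the trial or wastes much of its power. The documents do not support that. Random allocation from one stack is valid, the imbalance is due to chance, and the expected loss is small. Nor do they support saying that subtype comparisons would be adequate once stratified.

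**Conclusion.** The point holds as a low-priority design improvement. The protocol text leaves balance to chance on the one baseline factor its subgroup goal depends on, although that factor is known before randomisation. Under the assumed sizes, the chance that at least one subtype splits 2:1 or worse runs from 11% (equal subtypes, fixed stack) to 43% (60/20/10, simple randomisation). It is highest when one subtype is small.

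The conclusion rests on assumed subtype sizes, an unstated method of sequence generation, and the protocol text without its attachments. The differing ranks given to the subgroup comparison in sections 2a and 2b must be reconciled. The recommendation does not depend on which rank is kept.

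**What to change.** - Record each patient's subtype before any envelope is opened, so that the label cannot respond to the allocation.
- Replace the single stack with three numbered stacks of opaque envelopes, one per subtype, each prepared in permuted blocks of randomly varying size. State in section 3b how the sequence was generated.
- In section 3d, include subtype as a term in the two-month drug comparison.
- Reconcile the ranking of the subgroup goal between 2a and the two paragraphs of 2b.

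If envelopes are already in use, leave the allocation as it is and make the analysis change alone, together with the wording.

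The cost is preparing three stacks instead of one, with no extra patients, visits or staff. The downsides are a few incomplete blocks at the end of recruitment, which count for more in a small subtype, and the care needed to open the right stack.

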opening the lowest numbered of a stack of envelopes which will contain a randomly preselected card indicating which drug is to be used. The nortriptyline will be given in an escalating fashion, starting at 25 mg PO qhs for 2 weeks, followed by 50 mg PO qhs for 2 weeks, and finally 75 mg PO qhs. Patients will be encouraged to use the lowest effective dose and to self-titrate their medication. Topiramate dosing will be 25 mg PO qhs for 1 week, followed by 25 mg BID for 1 week, followed by 25 mg in the morning and 50 mg qhs for 1 week, and finally 50 mg BID. Patients will be allowed considerable leeway in adjusting their dosage and will be encouraged to stay on the lowest effective dose. Medication will be provided open label to the patient and paid for through the patients' insurance, as this intervention falls within current standard practice, and is not investigational.

After two, three and four months on drug patients will be brought into the clinic for a office visit or contacted by phone with history, and will complete MSQ V2.1, DHI, C-SSRS and the MoSQ, then patients will be offered the opportunity to switch to the other drug. Those patients who wish to switch drugs will first be weaned off their current drug over a one week time period. Patients who elect to stay on their initial drug will be followed for a total of four months. Patients who opt for trial of a second drug will then be started on the second drug via a self-titrating protocol as described above and followed on that drug for up to 4 months.

Our clinical experience has shown that on occasion patients will refuse to take more than a few doses of nortriptyline or topiramate due to intolerable side effects. Such patients will be allowed to immediately initiate therapy with the other drug. The medication change can be done with a phone call to their pharmacy without an office visit, as is done in standard of care. Also, patients who already follow a rigorous migraine diet will be allowed to enter the drug treatment phase immediately. In our experience, such patient make up less than 5% of the population that presents for treatment of vestibular migraine.

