5. Describe any risks related to performing study procedures. Please include all investigational, non-

Protocol Title: A Prospective randomized cross-over trial of nortriptyline and topiramate in the initial treatment of vestibular migraine

investigational, and non-invasive procedures (e.g., surgery, blood draws, treadmill tests).

n/a

6. Describe any risks related to the use of radioisotopes/radiation-producing machines (e.g., X-rays, CT scans, fluoroscopy).

7. Describe why this investigational compound/drug/device/procedure's risks/benefits are potentially better than standard of care or other common alternatives. Any standard treatment that is being withheld must be disclosed and the information must be included in the consent form. *?HELP?*

This drug is standard of care so the risks/benefits are identical to that of standard of care.

8. Describe any psychological, social, or legal risks the subject may experience. *?HELP?*

Risk of Questionnaires:

Some questions on the questionnaires may make patients feel uncomfortable, they may not answer any question they do not feel comfortable answering

Loss of Confidentiality

Page numbers from a sponsor's protocol/grant may be referenced in 9.9 and 9.10.

9. Special Precautions. Describe the planned procedures for protecting against or minimizing potential risks. If appropriate, include the standards for termination of the participation of the individual subject. Discuss plans for ensuring necessary medical or professional intervention in the event of adverse effects to the subjects.

Patients will be closely followed while they are on study and can stop or change medications if they do not like the medications effects that they are on. You will be given the Columbia Suicide Severity Rating Scale at each appointment to evaluate any changes in mood and behavior related to suicidal thoughts. [name] will be available to evaluate and treat or refer to a specialist for any adverse reactions.

10. Reproductive Risks.

a. Please list the pregnancy category of any drugs or N/A.

D

Protocol Title: A Prospective randomized cross-over trial of nortriptyline and topiramate in the initial treatment of vestibular migraine

b. Please describe any reproductive risk associated with any part of the research study. Include any data from other studies (animal or human).

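### Section 3b gives two on-drug assessment schedules and so does not settle whether patients are assessed one month after starting a drug

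*Combined protocol and SAP*

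**What the plan says.** All references are to the combined protocol and SAP.

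- **Start of drug (3b).** The last assessment before drug is at the end of the diet lead-in, when patients are randomised: "At the one month point, patients will be brought into the clinic for a office visit or contacted by phone and will complete medical history", together with the MSQ, DHI, C-SSRS and MoSQ.
- **On-drug contacts, first statement (3b).** "After two, three and four months on drug patients will be brought into the clinic for a office visit or contacted by phone". At these contacts patients "will complete MSQ V2.1, DHI, C-SSRS and the MoSQ, then patients will be offered the opportunity to switch to the other drug".
- **On-drug contacts, second statement (3b, two paragraphs later).** "The response to therapy will be assessed during monthly visits with the use of the MSQ, DHI and MoSQ questionnaires". The C-SSRS is not named here.
- **Suicide scale (9.9, Special Precautions).** "You will be given the Columbia Suicide Severity Rating Scale at each appointment". Its frequency therefore follows whichever visit schedule applies.
- **Early switching (2a and 3b).** In the first 8 weeks, patients who do not tolerate the first drug are told that "they can be switched to the other drug at any point". Section 3b lets the change be made through the pharmacy by telephone, with no office visit. No section asks for a questionnaire at that moment.
- **Analysis (3d).** Repeated measures ANOVA for change in MSQ and DHI, with no time points listed, and a cross-over comparison of each subject's DHI change on the two drugs.

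**The concern.** The two statements in 3b cannot both be a complete description of follow-up. Staff who follow the first would make no assessment until two months on drug. Staff who follow the second would make one at month one.

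Two things depend on the answer. The first is safety data. Section 9.3 lists suicide among the possible reactions to nortriptyline and suicidal behaviour and ideation among those to topiramate, and the safeguard in 9.9 is close follow-up with the C-SSRS at appointments. Section 9.11 states that there is neither a monitoring board nor a data safety monitoring plan, so the visit schedule carries much of the weight. The second is the efficacy data on the assigned drug. The cross-over analysis needs a DHI score on each drug, and the repeated measures analysis needs a fixed set of times.

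**Working it through.** **1. The plan's own figure.** Section 3b states 82% power for 45 per group, 60% against 30%, with a two-sided pooled Z-test at alpha 0.05.

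- Pooled proportion = (0.60 + 0.30)/2 = 0.45.
- Null standard error = √(2 × 0.45 × 0.55/45) = 0.1049.
- Alternative standard error = √((0.60 × 0.40 + 0.30 × 0.70)/45) = 0.1000.
- z = (0.30 − 1.96 × 0.1049)/0.1000 = 0.944, so power = 82.75%.

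The stated figure reproduces. It concerns an outcome after two months of medication, a time that both schedules include, so nothing below changes it.

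**2. Length of scheduled titration (3b).** Nortriptyline is given "starting at 25 mg PO qhs for 2 weeks, followed by 50 mg PO qhs for 2 weeks, and finally 75 mg PO qhs", so the top step starts after 2 + 2 = 4 weeks. Topiramate has three one-week steps before its last, so the top step starts after 1 + 1 + 1 = 3 weeks. These are the scheduled steps for the first drug only. Patients may also adjust their own dose, and a second drug has its own titration.

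**3. First on-drug assessment under each statement.** The documents do not define a month in weeks. I take 4 weeks, or a calendar month of 365.25/12/7 = 4.35 weeks.

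| | Two, three and four months | Monthly |
|---|---|---|
| First on-drug assessment | week 8.0 to 8.7 | week 4.0 to 4.3 |
| After end of nortriptyline titration (week 4) | 4.0 to 4.7 weeks | 0 to 0.3 weeks |
| After end of topiramate titration (week 3) | 5.0 to 5.7 weeks | 1.0 to 1.3 weeks |
| Position in the 8-week switch window | at or after its close | about midway |
| On-drug scores up to month two | 1 | 2 |
| On-drug scores up to month four | 3 | 4 |

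**4. Who is affected.** Sort patients by when they leave or switch from the first drug.

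- Before month one, including those who stop after a few doses: no scheduled first-drug score under either statement.
- Between months one and two: one first-drug score if visits are monthly, none under the other statement.
- After month two: at least one first-drug score under both.

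Only the middle group depends on the discrepancy. The documents give no rate of early switching or withdrawal, so its size cannot be calculated.

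**The case against.** The strongest reply is that monthly visits are plainly meant. The first statement does not say its contacts are the only ones. It ties them to the offer to switch, which fits the 8-week first period. Section 3b pays patients for each month, and 8i sends cheques monthly after each visit. Section 9.9 then brings the C-SSRS to every appointment. This has force, and it makes the monthly reading the more likely one. It does not remove the conflict. The first statement is the more specific, and it is the only on-drug one that names all four instruments. A month-one C-SSRS has to be inferred by joining 3b to 9.9.

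The months could also be study months, counted from the diet lead-in. But the text counts months on drug, and the five-month maximum in 8k fits one diet month plus four drug months. Study months would also bring the offer to switch after one month on drug, against the 8-week first period.

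The flow chart cited in 3b is not shown and may settle the matter. Its absence here is not counted against the plan, though the text would still need to agree with it.

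On safety, 3c promises close contact between physician and patient, and the attachments list a C-SSRS form covering the time since the last visit. A later visit could therefore recover information about the interval. That is not the same as timely detection, but the interval is not simply lost.

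**Conclusion.** The contradiction is real and should be corrected. Its consequence is conditional: if the two-, three- and four-month statement is followed as written, no questionnaire or suicide scale is scheduled from randomisation to about week 8, across the scheduled first-drug titration and the early-switch window. In the analysis, the loss is confined to patients who switch or leave between months one and two. It falls mainly on the cross-over comparison, which would lack their first-drug DHI, and on the repeated measures analysis.

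A reader might infer three stronger conclusions, none of which the documents support:

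- *That the trial definitely has an eight-week gap in suicide monitoring.* The monthly sentence, the monthly payments and 9.9 together point the other way.
- *That the main comparison is compromised.* The powered outcome is taken after two months on drug, and 2a keeps early switchers in follow-up on the other drug, so they can still be compared by assigned group.
- *That a stated number of patients would lose their data.* No early-loss rate is given, and those who stop after a few doses lack a first-drug score either way.

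The week figures rest on a month of 4 to 4.35 weeks.

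**What to change.** Reconcile the two statements in 3b, and 9.9, to a single schedule. It should list each on-drug time, the instruments taken at it, and explicitly whether the C-SSRS is among them. It should also say what, if anything, is recorded at an early switch and whether the on-drug month count restarts on the second drug. Which monitoring schedule to adopt is for the investigator and IRB.

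In 3d, name those times as the time points for MSQ and DHI, and replace repeated measures ANOVA with a mixed model that uses all available scores, so that patients with incomplete scores still contribute. This relies on the usual assumption that missingness is explained by the observed data. It cannot supply a first-drug score for patients who stop after a few doses, which the plan should acknowledge.

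The cost is wording in 3b, 3d and 9.9. If monthly visits are what was intended, no new procedure is added, since 3b and 8i already provide for monthly visits and payments. The sample size does not change.

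### Weight gain and weight loss are named side effects of the two drugs, but no weight is scheduled at randomisation or on drug, so the comparison rests on open-label report

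*Combined protocol and SAP*

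**What the plan says.** All of this is in section 3b (study procedures) of the combined protocol and SAP unless noted.

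- **Side effects.** For both drugs, "Specifically, the following known side effects will be asked about and recorded". The lists differ by drug: "Nortriptyline: somnolence, weight gain, dry mouth, blurred vision" and "Topiramate: Weight loss, parasthesias, forgetfulness, nausea, diarrhea, fatigue".
- **Entry.** At the first office visit, "patients height and weight (standard of care) will be obtained".
- **Diet lead-in.** "All drug naive patients will undergo a one month lead in of treatment involving dietary and behavioral control of migraine". It asks for "cessation of known migraine triggers such as caffeine, sodas, chocolates, alcohol (especially red wine) and aged cheeses". Patients controlled by diet who relapse between months 2 and 4 may start a drug then. Those already on a strict migraine diet, put at under 5%, may start at once.
- **Randomisation contact, month one.** Visit or phone, with medical history and four questionnaires. Weight is not listed.
- **On-drug contacts at two, three and four months.** "office visit or contacted by phone with history, and will complete MSQ V2.1, DHI, C-SSRS and the MoSQ". Weight is not listed.
- **Data list.** "Data which will be collected include age, sex, height, weight, body mass index (BMI" and further patient attributes follow, with no time point.
- **Blinding.** Medication is open label.
- **Analysis (section 3d).** It covers patient-reported effectiveness/acceptability, MSQ, DHI and a crossover comparison of DHI. It includes no analysis of weight or of adverse effects.

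**The concern.** Weight is the named side effect on which the two drugs are expected to move in opposite directions, and the trial already measures it objectively once. After entry it relies on what patients say. They know which drug they take, and the protocol lists a different direction for each drug. If the questions follow those lists, the arms do not even share a weight item: gain is asked under nortriptyline and loss under topiramate. Yet section 9.3 gives weight change in either direction as a possible reaction to nortriptyline.

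At stake is the tolerability comparison. A reported difference in weight effects could reflect the drugs, the patients' expectations or the wording of the lists, and no scheduled measurement would help to tell these apart.

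**Working it through.** **The plan's own figure.** The only computed figure is the 82% power for effectiveness/acceptability (section 3b: 45 per group, 60% versus 30%, two-sided alpha 0.05, pooled Z-test).

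- Pooled proportion 0.45. Null SE = sqrt(2 × 0.45 × 0.55 / 45) = 0.1049. Alternative SE = sqrt((0.24 + 0.21) / 45) = 0.1000.
- Power = Φ((0.30 − 1.96 × 0.1049) / 0.1000) = Φ(0.944) = 82.8%.

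This reproduces the stated 82%. The weight point does not depend on it.

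**Count of scheduled weights.**

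| Contact | Phone allowed | Weight listed |
|---|---|---|
| Entry | no, office visit | yes |
| Month one, randomisation | yes | no |
| Two, three, four months on drug | yes | no |
| Early switch for intolerance | yes, no visit needed | no |

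A within-patient change needs two weights. The schedule gives one, so no change on either drug can be computed from scheduled data.

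**What the entry weight could support if an on-drug weight were added.** Let W0 be weight at entry, W1 at randomisation and W2 at two months on drug. Then W2 − W0 = (W1 − W0) + (W2 − W1).

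- *Between drugs.* The first term, change over the diet period, arises before allocation and has the same expectation in both arms. It cancels in the between-arm difference, so there is no diet bias.
- *Precision.* Its variance does not cancel. If the diet-period change had the same SD as the on-drug change and were independent of it (an assumption), the half-widths below would rise by sqrt(2).
- *Within a drug.* The mean of W2 − W0 in one arm is diet change plus drug change, over a lag that varies from none (patients already on the diet) to about four months (late diet failures). It does not isolate the drug.

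**Precision with 45 per arm, all observed.** The documents give no SD for weight change. Assume 3 kg, range 2 to 5 kg. The 95% half-width for the difference in mean change is 1.96 × SD × sqrt(2/45).

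| Assumed SD (kg) | From randomisation weight (kg) | From entry weight, equal diet SD assumed (kg) |
|---|---|---|
| 2 | 0.83 | 1.17 |
| 3 | 1.24 | 1.75 |
| 5 | 2.07 | 2.92 |

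For a yes/no report made by a proportion p in each arm, the half-width is 1.96 × sqrt(2p(1 − p)/45): 16.5 percentage points at p = 0.2 and 20.7 at p = 0.5. Kilograms and percentage points are different scales, so these figures describe each measure and do not rank them.

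**The case against.** The strongest reply is that weight is not an outcome. The aims concern effectiveness, section 3d analyses no weight data, and section 3f calls both drugs standard of care. Asking about known side effects is an ordinary choice for a small open-label trial, and monthly contacts keep recall short. This stands as to priority: no planned efficacy conclusion or power figure changes.

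Repeat weights may also exist. The data list gives weight no time point, entry weight is labelled standard of care, some contacts will be office visits, and the flow chart and attached forms were not available to check. This stands in part: such weights are not ruled out, but nothing in the text requires or uses them, and a phone contact cannot yield a clinic weight.

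A reader might go further and infer that the diet month biases the drug comparison. It does not, because it precedes randomisation. Nor does every entry weight precede a diet month: some patients start a drug at once, and section 13 allows enrolment after diet changes have been tried. A reader might also infer a known amount of expectation bias. The documents give neither the wording of the question nor any figure for bias, so it is a plausible risk of unknown size.

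Finally, a home-scale reading is still a report from an unblinded patient. That is correct, and the fix has to allow for it.

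**Conclusion.** The point holds as a minor one. The plan commits to assessing opposite-direction weight effects but schedules one weight, at entry, and none at randomisation or on drug. The drug comparison on weight therefore rests on open-label answers to drug-specific questions, for an effect that could be measured at contacts already planned.

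If measured from randomisation, the difference in mean change would have a half-width of about 1.2 kg at an assumed SD of 3 kg (0.8 to 2.1 kg for 2 to 5 kg). That takes all 45 per arm as observed and ignores early switching. Missing weights would widen the interval. Switching would draw a comparison by randomised drug towards zero if the drugs act in the opposite directions the protocol names.

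The documents do not support saying that diet confounds the randomised comparison, that kilograms are shown to be more informative than yes/no reports, or that the primary comparison is undermined.

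**What to change.** 1. Record weight at the randomisation contact, at each on-drug contact and before any switch. Use the clinic scale at office visits and a home-scale reading at phone contacts. Note the source, and use the same scale within a patient where possible.
2. Report the difference between drugs in weight change from randomisation to the two-month contact, by randomised drug, with a 95% interval. State how many patients had switched by then. Add a sensitivity analysis using clinic weights only.
3. Summarise post-switch weights separately, as change from the pre-switch weight, by drug taken. Pooling them by randomised drug would blend the two drugs.
4. Ask the same weight question, covering both gain and loss, in both arms as a supplement.

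The cost is one number at contacts that already take place, one extra form field for the source, and a short addition to section 3d. The downsides are that home readings are noisier and remain patient-reported, mixing scales within a patient can add systematic error, and phone contacts, including switches arranged by phone, may leave some weights missing.
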